5.3 Treatment of subjects

Subjects will undergo a 12-week run-in period during which they will receive counselling in healthy nutrition and physical activity. This counselling will continue throughout the 56-week blinded period and the 26-week off-study-drug follow-up period.

Subjects who are eligible for randomisation will be administered liraglutide or placebo by a once-daily s.c. injections. Placebo contains the same excipients as liraglutide, but no active drug substance. Subjects randomised to receive placebo will receive s.c. injections with injection volumes corresponding to the liraglutide dose.

The injections can be done either in the abdomen, thigh, or upper arm. Injection region consistency is not required throughout the trial.

Injections can be administered at any time of day irrespective of meals. It is recommended that the time of injection for a subject is consistent throughout the trial.

Based on the results of the NN8022-3967 PK trial in pubertal adolescents with obesity (aged 12-17 years), including model-estimated steady-state exposure, treatment with liraglutide will be initiated with 0.6 mg daily for one week and increased in weekly steps of 0.6 mg until a maximum tolerated dose (MTD) or the 3.0 mg dose of liraglutide (highest allowed liraglutide dose) is reached. Dose escalation will be based on tolerability as judged by the investigator and the duration will be from 4-8 weeks (see Section [8.1.8.1](#)).

Subjects and their legally acceptable representative (LAR) will be instructed in symptom recognition and handling of hypoglycaemia, and in blood glucose measurements at randomisation (see Section [8.4.13](#)).

Medications that should not be used within 90 days before screening and during the trial are listed in Sections [6.3](#) and [6.5](#).

Subjects who at screening have a diagnose of T2DM can enter the trial. The only allowed anti-diabetic treatment is metformin.

If a subject develops T2DM ([Table 5–1](#)) during the course of the trial, he/she will be allowed to remain on trial product if glycaemic control can be achieved through healthy nutrition and physical activity, according to local standard of care. Furthermore, additional treatment with metformin is allowed, at the discretion of the investigator.

If diabetes treatment other than healthy nutrition, physical activity and metformin is required for glycaemic control, the trial product must be discontinued (see Sections [6.5](#) and [8.1.10](#)).

If a dose is missed, treatment should be resumed as prescribed at the next scheduled dose. An extra dose or increase in dose should not be taken for the missed dose. If more than 3 consecutive days have elapsed since the last dose, subject should resume dosing at the discretion and direction of the investigator.

5.4 Treatment after discontinuation of trial product

In the 26-week off-study-drug follow-up period, subjects will continue to receive counselling in healthy nutrition and physical activity.

After the end of the trial, subjects will be encouraged to continue following healthy nutrition and physical activity guidance, at the discretion of their healthcare provider. If trial product is discontinued prematurely (see Sections [6.5](#) and [8.1.10](#)), this also applies.

5.5 Rationale for treatment

As liraglutide will be administered by s.c. injections the same route of administration will be used for placebo in order to maintain blinding. The relatively slow absorption and half-life of approximately 13 hours make liraglutide suitable for once-daily administration, at any time of the day^{[22, 23](#)}.

The 3.0 mg dose of liraglutide is chosen as the target maintenance dose in the present trial. In the phase 2 dose-finding trial (NN8022-1807) in adults, the 3.0 mg dose of liraglutide (as adjunct to diet and exercise) was the most efficacious in terms of weight loss and improvements in cardiometabolic and quality of life endpoints. The safety profile of liraglutide 3.0 mg was generally similar to that of liraglutide at lower doses; the only types of AEs found to be dose-dependent were gastrointestinal disorders that were generally transient. In the subsequent phase 3 trials, liraglutide 3.0 mg, as an adjunct to a reduced calorie diet along with increased physical activity, induced a mean weight loss from baseline of $\geq 5\%$ that was superior to placebo (i.e., diet and exercise alone). Weight loss with liraglutide 3.0 mg was accompanied by positive effects on multiple glycaemic and non-glycaemic secondary endpoints.

Clinical trials in adults with or without obesity and with or without T2DM have demonstrated that liraglutide should be initiated at a daily dose of 0.6 mg, with subsequent dose escalation in 0.6 mg weekly increments in order to improve gastrointestinal tolerability. Based on the results of the NN8022-3967 PK trial in adolescents with obesity aged 12-17 years, liraglutide treatment will be initiated at the 0.6 mg dose and will be escalated in weekly increments of 0.6 mg. Given the more vulnerable nature of the paediatric population, the liraglutide dose will be escalated only if the present dose is tolerated.

In case of tolerability issues, the investigator has an option of prolonging the dose escalation period or reducing the trial product dose as described in Section [8.1.8.1](#). The dose may also be reduced to previous dose level in case of intermittent illness as described in Section [8.1.8.2](#).

Lifestyle modification is the recommended first-line treatment for overweight/obesity in the paediatric population^{[15,16](#)}. Therefore a 12-week run-in period with structured counselling in healthy nutrition and physical activity is included in the trial. Only subjects who, after this lifestyle modification attempt, still fulfil the definition of obesity can be randomised (as defined by inclusion

Protocol
Trial ID: NN8022-4180
UTN: U1111-1162-7101
EudraCT no.: 2014-004353-14

~~CONFIDENTIAL~~

Date: 01 June 2016
Version: 1.0
Status: Final
Page: 30 of 110

Novo Nordisk

and randomisation criteria). Currently, no pharmacologic agents are approved for weight management in the paediatric population with obesity in the European Union. Although orlistat has FDA approval for the above-mentioned indication in adolescents aged ≥ 12 years, its weight loss efficacy is modest and treatment compliance is low due to gastrointestinal adverse effects¹⁷⁻¹⁹. Therefore, a placebo comparator group will be used to evaluate whether liraglutide, in combination with healthy nutrition and physical activity, is more efficacious for the treatment of obesity than healthy nutrition and physical activity alone.

6 Trial population

6.1 Number of subjects

Number of subjects planned to be screened: 342

Number of subjects planned to be randomised: 228 (~ 33% screening failure rate)

For Mexico only: Out of the 228 subjects, approximately 40 subjects are planned to be randomised in Mexico.

6.2 Inclusion criteria

For an eligible subject, all inclusion criteria must be answered “yes”.

1. Informed consent obtained before any trial-related activities. Trial-related activities are any procedures that are carried out as part of the trial, including activities to determine suitability for the trial.
2. Male or female, age 12 to less than 18 years at the time of signing informed consent and less than 18 years at date of randomisation
3. BMI corresponding to ≥ 30 kg/m² for adults by international cut-off points and \geq the 95th percentile for age and sex (for diagnosis of obesity)
4. Stable body weight during the previous 90 days before screening V2 (<5 kg self-reported weight change)
5. History of failing to lose sufficient weight with lifestyle modification as judged by the investigator and documented in subject’s medical record

6.3 Exclusion criteria

For an eligible subject, all exclusion criteria must be answered "no".

1. Pre-pubertal subjects (Tanner stage 1) at screening V2
2. Body weight \leq 60 kg
3. Type 1 diabetes mellitus
4. Calcitonin ≥ 50 ng/L
5. Family or personal history of multiple endocrine neoplasia type 2 (MEN2)
6. Medullary thyroid carcinoma (MTC)
7. History of pancreatitis (acute or chronic)
8. Subjects with secondary causes of obesity (i.e., hypothalamic, genetic or endocrine causes)
9. Treatment with medications within 90 days before screening V2 that, based on the investigator’s judgement, may cause significant weight change. This should also include treatment with any of

the following medications: pramlintide, orlistat, zonisamide, topiramate, lorcaserin, phentermine, bupropion, naltrexone, GLP-1 receptor agonists, or metformin (used as treatment for obesity)

10. Anti-diabetic treatment other than metformin
11. Diet attempts using herbal supplements or over-the-counter medications within 90 days before screening V2
12. Participation in an organised weight reduction program (e.g., Weight Watchers[®]) within 90 days before screening V2
13. Previous surgical treatment for obesity (excluding liposuction if performed >1 year before screening V2)
14. History of major depressive disorder within 2 years before screening V2
15. Any lifetime history of other severe psychiatric disorder (e.g., schizophrenia, bipolar disorder)
16. PHQ-9 score of ≥ 15 at screening V2
17. Any suicidal ideation of type 4 or 5 based on the baseline C-SSRS questionnaire at screening V2
18. Any suicidal behaviour within 30 days before screening V2
19. Any lifetime history of suicidal attempt
20. Uncontrolled treated or untreated hypertension >99th percentile for age and gender in children. If white-coat hypertension is suspected at screening V2, a repeated measurement at V3 prior to other trial-related activities is allowed (last measurement being conclusive)
21. Surgery scheduled for the trial duration period, except for minor surgical procedures, at the discretion of the investigator
22. Subjects with confirmed bulimia nervosa disorder
23. Diagnosis of malignant neoplasms within the last 5 years prior to screening V2 (except basal and squamous cell skin cancer)
24. Known or suspected abuse of alcohol or narcotics
25. Language barrier, mental incapacity, unwillingness or inability to adequately understand or comply with study procedures
26. Known or suspected hypersensitivity to trial product or related products
27. Previous participation in this trial. Participation is defined as signed informed consent.
28. Subjects from the same household participating in the trial
29. Participation in any clinical trial of an approved or non-approved investigational medicinal product within 30 days before screening V2
30. Female who is pregnant, breast-feeding or intends to become pregnant or is of child-bearing potential and not using an adequate contraceptive method (adequate contraceptive measure as required by local regulation or practice)

For Sweden only: Oral (except low-dose gestagen [lynestrenol and norethisteron]), injectable, or implanted hormonal contraceptives, intrauterine device, intrauterine system (for example, progestin-releasing coil), vasectomized male (with appropriate postvasectomy documentation of the absence of sperm in the ejaculate). Use of contraception is not required for female subjects who have not yet made their sexual debut and/or are not sexually active.

For Belgium only: Highly effective methods of birth control are defined as those, alone or in combination, that result in a low failure rate (i.e., less than 1% per year) when used consistently and correctly; such as implants, injectables, combined oral contraceptives, some intrauterine devices, true sexual abstinence (i.e., refraining from heterosexual intercourse during the entire period of risk associated with the study treatments) or vasectomised partner.

31. Any condition which, in the opinion of the investigator, might jeopardise subject's safety or compliance with the protocol

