This is a 56-week double-blind, randomised, parallel-group, placebo-controlled, multi-national trial followed by a 26-week period off study-drug. The trial will be conducted in pubertal adolescents with obesity aged 12 to less than 18 years. Subjects will be randomised 1:1 to receive liraglutide or placebo. The randomisation will be stratified according to pubertal and glycaemic status.

At least 30% of subjects will be from areas with lifestyle and nutrition comparable to those in the European Union. All subjects will undergo counselling in healthy nutrition and physical activity for weight loss and must be prescribed a structured programme from the beginning of the 12-week run-in period and continuing through the 26-week follow-up period off trial drug.

Trial population:

A planned total of approximately 342 subjects will be screened. A planned total of 228 subjects will be randomised.

Key inclusion criteria:

- Informed consent obtained before any trial-related activities. Trial-related activities are any procedures that are carried out as part of the trial, including activities to determine suitability for the trial.
- Male or female, age 12 to less than 18 years at the time of signing informed consent and less than 18 years at date of randomisation
- BMI corresponding to ≥ 30 kg/m² for adults by international cut-off points and \geq the 95th percentile for age and sex (for diagnosis of obesity)
- Stable body weight during the previous 90 days before screening V2 (<5 kg self-reported weight change)
- History of failing to lose sufficient weight with lifestyle modification as judged by the investigator and documented in subject's medical record

Key exclusion criteria:

- Pre-pubertal subjects (Tanner stage 1) at screening V2
- Type 1 diabetes mellitus (T1DM)
- Family or personal history of multiple endocrine neoplasia type 2 (MEN2)
- Medullary thyroid carcinoma (MTC)
- History of pancreatitis (acute or chronic)
- Subjects with secondary causes of obesity (i.e., hypothalamic, genetic or endocrine causes)
- Treatment with medications within 90 days before screening V2 that, based on the investigator's judgement, may cause significant weight change. This should also include treatment with any of the following medications: pramlintide, orlistat, zonisamide, topiramate, lorcaserin, phentermine, bupropion, naltrexone, glucagon-like peptide-1 (GLP-1) receptor agonists, or metformin (used as treatment for obesity)

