6.5 Criteria for premature discontinuation of trial product

Efforts must be made so that subjects attend and complete all scheduled visit procedures. Randomised subjects should stay in the trial irrespective of lack of adherence to randomised treatment, lack of adherence to visit schedule or missing assessments. Only in case a subject or subject's LAR decline any further contact with the site in relation to the trial this will be considered as withdrawn from the trial.

The subject may be prematurely discontinued from trial product, at the discretion of the investigator, due to a safety concern. The subject must be prematurely discontinued from trial product if the following applies:

1. Safety concern (not covered by any of below criteria) or unacceptable intolerability to trial product, as judge by the investigator.
2. Included in the trial in violation of the inclusion and/or exclusion criteria and/or randomisation criteria
3. Pregnancy
4. Intention of becoming pregnant
5. In case of code break (see Section [11.1](#))
6. Suspicion of pancreatitis (see Sections [8.4.10.5](#) and [8.4.11](#)). Subjects may restart on trial product should the suspicion not be confirmed.
7. Diagnosis of medullary thyroid carcinoma
8. Weight loss attempts other than what is agreed with the dietitian as part of the trial intervention
9. If diabetes treatment other than healthy nutrition, physical activity and metformin addition is initiated.

10. Initiation of treatment with medications that, based on the investigator's judgement, may cause significant weight change. This should also include treatment with any of the following medications: pramlintide, orlistat, zonisamide, topiramate, lorcaserin, phentermine, bupropion, naltrexone, GLP-1 receptor agonists, or metformin (used as treatment for obesity)
11. Anti-diabetic treatment other than metformin
12. Initiation of diet attempts using herbal supplements or over-the-counter medications
13. Inadequate psycho- and/or pharmaco therapeutic treatment of a subject's psychiatric disorder (see Section [8.4.9.3](#))
14. The subject and/or the subject's LAR refusal of referral to a mental health professional (MHP) and it, in investigator's opinion, is unsafe for the subject to continue in the trial (see Section [8.4.9.3](#))
15. Simultaneous participation in another clinical trial of an approved or non-approved investigational medicinal product

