8.1.4 Run-in visits

Subject's eligibility according to the in- and exclusion criteria must be evaluated before the 12-week run-in period is initiated.

V4 and V6 can be performed as phone visits. All subjects must be reminded to attend V8 and the randomisation visit in a fasting state.

During the run-in period the investigator should evaluate the subject's compliance with the run-in procedures and visit schedule. If deemed acceptable, as judged by the investigator, the subject can proceed to randomisation visit. If not, the subject is a screening failure ([8.1.5](#)).

All run-in assessments as described in Section [2](#) must be performed and data recorded in the eCRF. For screening failures, please refer to Section [8.1.5](#).

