8.1.5 Screening failures

A screening failure is a subject who does not fulfil one or more of the inclusion and/or exclusion and/or randomisation criteria. For screening failures the screening failure form in the electronic case report form (eCRF) must be completed with the reason for not continuing in the trial. Serious adverse events (SAE) from screening failures must be transcribed by the investigator into the eCRF. Follow-up on SAEs must be carried out according to Section [12](#). A screening failure session must be made in the IWRS. The case book must be signed.

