In order to improve gastrointestinal tolerability of liraglutide, a weekly dose-escalation scheme will be used during the initial 4-8 weeks. In contrast to the scheme used for adult subjects, for adolescent subjects, the trial product dose will be escalated only if the previous dose is tolerated (as judged by the investigator). Furthermore, to resolve tolerability issues, the investigator is allowed to lower to the previously given dose or to prolong a dose step for one additional week (see Section [8.1.8.1](#)). Subjects treated with trial product should be advised of the potential risk of dehydration, renal impairment and acute renal failure, in relation to gastrointestinal AEs and take precautions to avoid fluid depletion.

Hypoglycaemic episodes will be assessed in this trial as part of routine safety monitoring. If a subject develops T2DM during the trial, he/she will be allowed to remain in the trial if glycaemic control can be achieved with healthy nutrition, physical activity and metformin.

Subjects with a history of acute or chronic pancreatitis will be excluded from trial participation. Trial participants will be informed of the characteristic symptoms of acute pancreatitis. Furthermore, serum lipase and amylase activity levels will be monitored on a regular basis during the course of the trial. If pancreatitis is suspected, the trial product should promptly be interrupted until the presences of pancreatitis can be excluded (see Section [8.4.11](#)) and appropriate treatment should be initiated. Subjects that are diagnosed with acute pancreatitis must have their trial product discontinued. Subjects with a personal or family history of MTC and subjects with MEN2 are excluded from this trial. In addition, subjects with a screening calcitonin (a specific biomarker for C-cell activation) level ≥ 50 ng/L will be excluded from the trial as hormone concentrations above this threshold are indicative of C-cell neoplasia. During the trial, calcitonin levels will be measured at pre-specified trial visits and levels above ULN will be flagged by the laboratory, and reported to the investigator and Novo Nordisk.

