Appendix C

Liraglutide NN8022-4180

Calcitonin Monitoring

Table of Contents

	Page
Table of Contents	2
1 Background.....	3
2 Calcitonin and C-cell abnormalities - evaluation and follow-up	4
3 References	5

1 Background

Non-clinical experiments conducted in rodents have demonstrated that liraglutide has the potential to stimulate growth and proliferation of thyroid C-cells. It is unknown whether liraglutide causes thyroid C-cell neoplasms, including medullar thyroid carcinoma (MTC) in humans, as human relevance could not be ruled out by clinical or nonclinical studies.

However, based on the findings in rodents, monitoring of serum calcitonin (a sensitive biomarker for C-cell activation) is currently being performed in clinical trials with liraglutide.

While there is general agreement on the clinical interpretation of substantially elevated calcitonin levels (greater than 100 ng/L) as likely indicative of C-cell neoplasia¹, the interpretation of values between the upper limit of normal and 100 ng/L can become problematic.

There is little information available on normal calcitonin levels in children. The available information suggests that children in the age range included in this clinical trial (12 to less than 18 years) will have calcitonin levels indistinguishable from adults².

There are several known factors affecting calcitonin levels, namely renal dysfunction, smoking, several drug classes (proton pump inhibitors, beta-blockers, insulin secretagogues). Physiology of C-cell activation in various clinical conditions and in different patient populations (i.e., with various co-morbidities) is poorly understood. There may be various clinical conditions not identified so far which mildly or moderately affect calcitonin secretion by C-cells.

2 Calcitonin and C-cell abnormalities - evaluation and follow-up

Subjects with a personal or family history of MTC or multiple endocrine neoplasia syndrome type 2 (MEN 2) or with a screening calcitonin ≥ 50 ng/L at V2 must be excluded from the trial.

Subjects who are screen failures and have a calcitonin level above the normal range should be referred to their primary care physician and consideration given to referring the subject to a paediatric endocrinologist or thyroid specialist for further evaluation.

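### Exclusion criterion 6 names only MTC and omits the family history that Section 18.1 and Appendix C require sites to exclude

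*Protocol*

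**What the plan says.** Section 6.3 of the protocol makes a subject eligible only if every numbered exclusion criterion is answered no. Criterion 5 reads "Family or personal history of multiple endocrine neoplasia type 2 (MEN2". Criterion 6, directly below it, reads "6. Medullary thyroid carcinoma (MTC" and goes no further. The key exclusion criteria in Section 1 follow the same pattern: the MEN2 bullet carries the history wording, and the next bullet is simply "Medullary thyroid carcinoma (MTC".

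Two other places go further. Section 18.1, under trial-specific risk mitigation, states: "Subjects with a personal or family history of MTC and subjects with MEN2 are excluded from this trial". Appendix C, section 2, names "Subjects with a personal or family history of MTC or multiple endocrine neoplasia syndrome type 2 (MEN 2", together with anyone whose calcitonin at V2 is 50 ng/L or more, as subjects who must be excluded.

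The amendment text provided does not touch criterion 6. The only change to Section 6.3 that it shows is to criterion 30 for Sweden, and the Mexico amendment lists no change to Section 6.3.

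**The concern.** The protocol describes two different populations. The benefit-risk section and Appendix C keep out adolescents with a family history of MTC; the numbered criteria do not mention them. Because criterion 5 spells out family history and criterion 6 does not, a site could reasonably take the difference as deliberate.

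This is a safety exclusion. Section 3.1 reports thyroid C-cell tumours in rats and mice at clinically relevant exposures, and Section 18.1 says that their relevance to humans has not been determined. Excluding people with a personal or family history of MTC is one of the measures that Section 18.1 offers against that risk. An ethics committee reading Section 18.1 is told that these minors are kept out, while the checklist that would keep them out does not say so.

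**Working it through.** No figure in the plan lies behind this point, so the check is a comparison of texts followed by a rough estimate of size.

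**1. Texts side by side**

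| Place | MEN2 | MTC |
|---|---|---|
| Section 1, key exclusion criteria | family or personal history | MTC only |
| Section 6.3, nos. 5 and 6 | family or personal history | MTC only |
| Section 18.1 | subjects with MEN2 | personal or family history |
| Appendix C, section 2 | personal or family history | personal or family history |

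Family history of MTC is excluded in two places and is absent from both lists of criteria. Personal MTC is reasonably covered by criterion 6 as it stands, and by criterion 23 if it was diagnosed within 5 years. The clear gap is family history.

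**2. A test case against the list**

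Take a subject with a relative who has MTC, no known MEN2 in the subject or family, and screening calcitonin below 50 ng/L.

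- Criterion 4 (calcitonin): no.
- Criterion 5 (MEN2): no.
- Criterion 6 (MTC): no.

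The downstream rules refer back to the criteria:

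- Section 8.1.4: "eligibility according to the in- and exclusion criteria must be evaluated before the 12-week run-in period is initiated".
- Section 8.1.5: "A screening failure is a subject who does not fulfil one or more of the inclusion and/or exclusion and/or randomisation criteria".
- Section 6.5, no. 2, requires trial product to be stopped for a subject "Included in the trial in violation of the inclusion and/or exclusion criteria and/or randomisation criteria".

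None of these is expressly triggered by the test case. Section 6.5, no. 7, applies only once MTC is diagnosed.

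**3. Would other text catch the subject?**

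- Section 6.3 does not refer to Appendix C. The body text points to Appendix C in Sections 8.4.12 and 8.5.4, both about raised calcitonin. The flowchart is incomplete in the text available, so this statement is limited to the body text.
- Section 8.2.2 defines medical history by the subject's own past events and does not ask about relatives.
- Criterion 31 could be used, but it depends on the investigator's opinion, as does Section 6.5, no. 1.
- Calcitonin review after randomisation, with expert referral at 20 ng/L or more (Section 8.4.12, Appendix C), acts after dosing has started.

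**4. Size**

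Inputs: n = 228 randomised and 342 screened (Section 6.1). The prevalence p of a known family history of MTC without known MEN2 is not in the documents; 1 in 100,000 to 1 in 1,000 is assumed.

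Expected number = n × p. Chance of at least one = 1 − (1 − p)^n.

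| p | Expected, n = 228 | At least one, n = 228 | Expected, n = 342 | At least one, n = 342 |
|---|---|---|---|---|
| 1 in 100,000 | 0.0023 | 0.23% | 0.0034 | 0.34% |
| 1 in 10,000 | 0.023 | 2.25% | 0.034 | 3.4% |
| 1 in 1,000 | 0.228 | 20.4% | 0.342 | 29.0% |

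These are chances that such a subject is present, not that one is wrongly dosed. Wrong dosing also needs normal calcitonin and a site that applies neither Appendix C nor Section 18.1 nor criterion 31.

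**The case against.** The strongest reply is that the exclusion is already in the protocol. Appendix C is part of it and uses mandatory language, Section 18.1 repeats the MTC exclusion, and Section 8.1 requires procedures to be carried out as the protocol describes, so a careful site would exclude the subject. Criterion 5 already makes the site take a family history at the same step, and the protocol pairs MEN2 with MTC wherever it states these exclusions. With several backstops and fewer than one subject expected, this could be called a minor matter of wording.

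Much of this stands. The intent is clear, the gap is one of drafting, and the expected number is very small, resting on an assumed range that spans a factor of 100. It does not remove the problem. Criterion 5 asks about MEN2, not MTC, and a family with MTC and no known MEN2 gives a truthful no. The backstops depend on raised calcitonin, on judgement, or on events after dosing has begun.

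It can also be said that Section 18.1 is itself loose, since it omits family history of MEN2. That is true but harmless, because criterion 5 carries that exclusion in the operative list. For MTC the position is reversed: the list is the narrower text.

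**Conclusion.** The concern holds. Criterion 6 and the Section 1 bullet are narrower than Section 18.1 and Appendix C, and the part left out, family history of MTC, is an exclusion that the protocol itself calls mandatory. The textual finding rests on no assumption. Only its size does: under the assumed prevalence, between 0.002 and 0.23 of the 228 randomised subjects would be affected. The primary endpoint, type I error, power and efficacy analysis are untouched. It should be fixed because a stated safeguard for minors is missing from the list that decides eligibility, not because many cases are expected.

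**What to change.** Reword criterion 6 in Section 6.3 and the matching bullet in Section 1 to *Family or personal history of medullary thyroid carcinoma (MTC)*. This brings both lists into line with Section 18.1 and Appendix C, and no other section has to change. Adding family history to the MEN2 wording in Section 18.1 would be tidy but is optional.

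The cost is a one-line amendment and the same change wherever sites record criterion 6 (that form is not in the documents). Under Section 25 the amendment needs ethics approval or a favourable opinion according to local regulations before use, and it goes to the regulatory authorities. Until then, a note to sites that Appendix C, section 2, already applies at screening would cover the gap. The recruitment loss is negligible: even at the top of the assumed range, fewer than one subject is expected among the 342 screened.
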